15.4 Exploratory Endpoint Analysis

15.4.1 Population Pharmacokinetics

Full details of the Population PK Analysis planned to be performed on data of the current study will be described in a separate Data Analysis Plan. The results of the M&S work will be described in a dedicated report, separately from the study CSR.

It will be eventually up to the CRO that does the M&S and the supervisor (Merck or not) to decide how to structure all the details of the planned modeling, in agreement with the team.

16 Safety Evaluation

Safety and tolerability of study treatment will be assessed by the examination of AEs, laboratory data, ECGs, vital signs, and PK data.

All summaries of safety data will be based on the SAF analysis set.

16.1 Adverse Events

Adverse events will be collected throughout the study and coded using version 19.1 of MedDRA or later.

Treatment-emergent adverse events (TEAEs) are those events that start on or after the day of first administration of study treatment. If an AE started on the same date as the first administration of the first study treatment given, the timing related to study treatment as recorded on the adverse events page of the eCRF will be taken into account when determining treatment emergence. A worst case approach will be used, ie if time is missing or if the AE occurred at the same time as the first administration of the first study treatment given, then the AE will be classified as treatment-emergent.

Incomplete AE-related dates will be handled as follows:

- In case the onset date is missing completely or missing partially but the onset month and year, or the onset year are equal to the start of study treatment then the onset date will be replaced by the minimum of start of study treatment and AE resolution date.
- In all other cases the missing onset day or missing onset month will be replaced by 1.
- Incomplete stop dates will be replaced by the last day of the month (if day is missing only), if not resulting in a date later than the date of subject's death. In the latter case the date of death will be used to impute the incomplete stop date.
- In all other cases the incomplete stop date will not be imputed.

Only TEAEs will be included in tables and will be summarized by treatment arm. All AEs will be listed.

Unless otherwise stated, TEAEs will be displayed in terms of frequency tables: primary SOC in alphabetical order, then PT in order of decreasing frequency across both treatment arms. If a subject has more than one event for a particular SOC or PT, then the event will be counted once only for the subject. For example, if a subject has two different TEAEs but these are within the same SOC, then they will be counted once for each PT but only once for the SOC. If at any time a summary is being prepared on data that are not fully coded, uncoded TEAEs will be summarized with a SOC as 'Uncoded' and the PT term will be set to the TEAE verbatim text.

If an AE is reported for a given subject more than once during treatment, the worst relationship to study treatment will be tabulated.

Adverse events related to study treatment are those events with relationship missing, unknown or yes.

Treatment-emergent AEs will be summarized by primary SOC, PT and worst toxicity grade (according to National Cancer Institute-Common Terminology Criteria for Adverse Events [NCI-CTCAE], version 4.03) per subject. In case a subject had events with missing and non-missing toxicity grades, the maximum of the non-missing toxicity grades will be displayed.

16.1.1 All Adverse Events

An overall summary table will present the number of subjects with at least one of the following TEAEs, summarized by treatment arm:

- TEAE
- Study drug related TEAE
- Serious TEAE
- Study drug related serious TEAE
- TEAE of NCI-CTCAE toxicity Grade 1
- TEAE of NCI-CTCAE toxicity Grade 2
- TEAE of NCI-CTCAE toxicity Grade 3
- TEAE of NCI-CTCAE toxicity Grade 4
- TEAE of NCI-CTCAE toxicity Grade 5
- TEAE of NCI-CTCAE toxicity Grade ≥ 3
- TEAE of NCI-CTCAE toxicity Grade ≥ 4
- Study drug related TEAE of NCI-CTCAE toxicity Grade 1
- Study drug related TEAE of NCI-CTCAE toxicity Grade 2
- Study drug related TEAE of NCI-CTCAE toxicity Grade 3
- Study drug related TEAE of NCI-CTCAE toxicity Grade 4
- Study drug related TEAE of NCI-CTCAE toxicity Grade 5
- Study drug related TEAE of NCI-CTCAE toxicity Grade ≥ 3
- Study drug related TEAE of NCI-CTCAE toxicity grade ≥ 4
- TEAE of special interest
- TEAE of special interest Grade 1
- TEAE of special interest Grade 2
- TEAE of special interest Grade 3
- TEAE of special interest Grade 4

- TEAE of special interest Grade 5
- Study drug related AESI
- Study drug related AESI Grade 1
- Study drug related AESI Grade 2
- Study drug related AESI Grade 3
- Study drug related AESI Grade 4
- Study drug related AESI Grade 5
- TEAE leading to death
- Study drug related TEAE leading to death.
- Injection Site Reactions

Incidence rates will be included in these overall summaries as the number of events per 100 subject-years of exposure to IMP, calculated as the number of subjects with AEs divided by the total time at risk across all subjects in the given treatment arm, multiplied by 100. Time at risk for a subject is calculated as time from first dose to 28 days following the last dose of IMP. Two-sided 95% CIs for incidence rates will be provided using the exact Poisson method.

The following frequency tables will be prepared by treatment arm, primary SOC in alphabetical order, then PT in order of decreasing frequency across both treatment arms:

- TEAEs
- Study Drug related TEAEs
- Serious TEAEs
- Non-serious TEAEs with frequency of $\geq 5\%$ in any treatment arm
- Non-serious TEAEs with frequency of $\geq 1\%$ in any treatment arm
- TEAE leading to death
- Study drug related TEAE leading to death
- TEAEs by NCI-CTCAE toxicity grade
- Study Drug related TEAEs by NCI-CTCAE grade
- TEAEs by worst NCI-CTCAE toxicity grade.
- Injection Site Reactions- Local Tolerability
- Study Drug Related Injection Site Reactions by NCI-CTCAE grade and duration
- Study Drug Related Injection Site Reactions by NCI-CTCAE grade and time since last study administration

Summary statistics will be presented for the following:

MSB11022 in Moderate to Severe Rheumatoid Arthritis version 3.0 Final

- Duration of study drug related injection site reactions (hours) calculated as the difference of start date/time and stop date/time divided by 3600 [(stop date/time start date/time)/3600]. If start time is missing then start time will be set to 00:00. If stop time is missing then stop time will be set to 23:59. Duration will not be calculated if start date or stop date are missing. If a subject has more than one study drug related injection site reactions then the event with the longest duration will be used.
- Number of subjects with duration of study drug related injection site reaction <24 hours, ≥ 24 < 48 hours and ≥ 48 hours. If a subject has more than one study drug related injection site reactions then the event with the longest duration will be used.
- Time since the first study treatment administration to the study drug related injection site reaction start date/time calculated as the difference of first study drug administration date/time and the injection site reaction start date/time divided by 3600 [(Injection site reaction start date/time First study drug administration date/time)/3600]. Time since the first study treatment administration will not be calculated if injection site reaction start date or first study drug administration date are missing. If first study treatment administration time is missing then it will be set to 23:59. If study drug related injection site reaction start time is missing then it will be set to 00:00. In the special cases that any time is missing and first study treatment administration date equals the study drug related injection site reaction start date then time since first study treatment administration will be set to 0. If a subject has more than one study drug related injection site reactions then the event with the shortest duration will be used.
- Number of subjects with time since the first study treatment administration to the study drug related injection site reaction <24 hours, ≥ 24 < 48 hours and ≥ 48 hours. If a subject has more than one study drug related injection site reactions then the event with the shortest duration will be used.
- Time since last study treatment administration to the study drug related injection site reaction start date/time calculated as the difference of the last study drug administration date/time and the study drug related injection site reaction start date/time divided by 3600 [(Injection site reaction start date/time Last study drug administration date/time)/3600]. Time since the last study treatment administration will not be calculated if study drug related injection site reaction start date or last study drug administration date are missing. If last study treatment administration time is missing then it will be set to 23:59. If injection site reaction start time is missing then it will be set to 00:00. In the special cases that any time is missing and last study treatment administration date equals injection site reaction start date then time since last study treatment administration will be set to 0. If a subject has more than one study drug related injection site reactions then the event with the shortest duration will be used.
- Number of subjects with time since the last study treatment administration to the injection site reaction <24 hours, ≥ 24 < 48 hours and ≥ 48 hours. If a subject has more than one study drug related injection site reactions then the event with the shortest duration will be used.
- Medication or procedure taken for study drug related injection site reactions. Frequencies and percentages will be based on the number of subjects.

Additionally the study drug related injection site reactions rate based on the overall number of study treatment injections administered will be calculated by SOC and PT.

The following frequency tales will be prepared by PT in order of decreasing frequency across both treatment arms:

- TEAEs with frequency of $\geq 5\%$ in any treatment arm
- TEAEs with frequency of $\geq 1\%$ in any treatment arm
- Treatment emergent AESIs (as per section 15.1).

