Patients who discontinue from study medication (but remain in the trial and continue for the safety/immunogenicity visits) before the Week 52 visit will immediately complete an Early Termination visit and return for a Safety/Follow-up visit four weeks after the last dose of IMP. During this 4-week Safety Follow-up period, no excluded treatment for RA (as defined in the protocol) should be administered. Patients will return for an additional safety evaluation four months after the last dose of IMP. Treatment for RA from the 4-week Safety Follow-up visit to the 4-month Safety Evaluation visit will be at the discretion of the Investigator following institutional standard of care. The 4-week and 4-month Safety Follow-up visits will not be duplicated if either of these visits falls within two weeks of an otherwise scheduled visit. If the 4-week and 4-month Safety Follow-up since last IMP are completed within the 52 week visit schedule, these will not be repeated thereafter.

All subjects will have PK samples taken pre-first dose, and then prior to dosing on Weeks 2, 4, 12, 24, 36 and 52. In addition, a subset of 60 subjects (30 per arm) will have additional samples to support the population PK analysis taken on Days 2 (24 h post first dose), 4, and 9, and Days 2 (24 h post Week 24 dose), 4, 9, and 14 (Week 26 pre dose) after the Week 24 dose.

The anticipated duration of the entire trial is approximately two years.

Visit schedules for safety, immunogenicity, and efficacy assessments are detailed in the

Schedule of Assessments in the protocol.

Planned number of patients: Approximately 260 randomized subjects

Primary endpoint:

• Treatment-emergent adverse events of special interest (AESI) including and up to Week 52

Secondary endpoints:

Key secondary endpoint

• American College of Rheumatology 20% response criteria (ACR20) at Week 12. An ACR20 response is defined as an improvement of at least 20% in the number of tender joints and swollen joints, and at least 20% improvement in three out of the remaining five ACR core-set measures: patient assessment of arthritis pain, Patient's and Physician's Global Assessment of Disease Activity, physical function via the Health Assessment Questionnaire-Disability Index [HAQ-DI] and acute-phase reactant as measured by C-reactive protein (CRP).

Other secondary endpoints

Safety

- Occurrences of treatment-emergent adverse events (TEAEs) and serious adverse events (SAEs) including and up to Week 52

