7.2 Randomization

Eligible subjects will be randomized in permuted blocks in a 1:1 ratio by an IWRS to receive either MSB11022-CCI sc or Humira sc at a dose of 40 mg every other week starting at baseline up to and including Week 48.

Randomization will be stratified by previous disease-modifying therapy use. Subjects will be stratified by the type of systemic therapy previously received: non-biological (biologic naïve subjects) versus biological (biologic experienced subjects). Subjects who previously received both (biological and non-biological systemic therapies) will be assigned to the "biological" group. The exposure to previous biological agents will be limited to one TNF inhibitor other than adalimumab. The participation of subjects in the previous biological systemic therapy stratum will be capped at 20% of the total number of subjects randomized.

8 Overview of Planned Analyses

Once the last subject has completed the 4-month safety follow-up visit, the database will be locked. The analysis will be performed using cleaned study data collected in electronic case report form (eCRF) or transferred from laboratories performing laboratory tests and biosample analysis until the date of the 4-month safety follow-up visit of the last subject. Once the data cleaning is complete, a data review meeting will be held prior to the database lock. In addition, no data can be frozen or locked and no randomization code should be unblinded until this Statistical Analysis Plan (SAP) has been approved.

The final analysis will include all data collected during the study up to week 52 date (or end of treatment date+28 days, whichever occurs later) for subjects who completed the study, and theoretical week 52 (ie 52 weeks after first intake) or 4 months safety follow-up visit, whichever occurs first, for subjects who early terminated the treatment.

All AE tables and listings will be re-produced to reflect any additional AEs and any updates to the reported AEs in final analysis. Additionally the concomitant medication and procedure tables and listings will be re-produced to reflect any updates.

In addition, an independent data monitoring committee (IDMC) will review safety and tolerability data of this study on an ongoing basis. The methodology and presentation of results for the IDMC are covered in the IDMC Charter and in Section 18.

9 Changes to the Planned Analyses in the Clinical Trial Protocol

Not applicable.

10 Protocol Deviations and Analysis Sets

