15.1 Primary Endpoint Analyses

The primary endpoint is the occurrence of treatment-emergent AESIs (hypersensitivity) up to Week 52.

The primary analysis will be based on the safety analysis set.

The following is considered pre-defined AESI for this trial:

Hypersensitivity (defined by Standardized MedDRA Queries [SMQs] narrow as per the latest MedDRA version).

The proportions of subjects with AESIs (hypersensitivity) and accompanying 95% CIs (Exact 95% CIs, calculated with the Clopper-Pearson method) will be provided for each treatment arm. Half width of 95% CIs for the difference between treatment arms in occurrence for the most commonly observed clinical events of AESI (hypersensitivity) will also be presented. The cut-off point for the selection of the most commonly observed clinical events will be decided prior to the database lock and the treatment unblinding.

Listings of all AESIs (hypersensitivity) and listings of AESIs (hypersensitivity) with NCI-CTCAE Grade \geq 3 will be provided.

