16.2.3 Other Significant Adverse Event

16.2.3.1 Adverse Events of Special Interest (AESIs)

The occurrence of treatment-emergent adverse events of special interest (hypersensitivity) up to Week 52 is the primary endpoint (see Section 15.1 for the analysis of these AEs).

The following is considered pre-defined AESI for this study:

Hypersensitivity (defined by Standardized MedDRA Query [SMQ] narrow as per the latest MedDRA version).

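### SAP 16.1.1 labels as an event rate a ratio of affected subjects to time at risk that does not stop at the first event, and sets no matching window for the events counted

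*SAP*

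**What the plan says.** SAP 16.1.1 adds a rate to the overall adverse event summary: "Incidence rates will be included in these overall summaries as the number of events per 100 subject-years of exposure to IMP". The same sentence then defines it, before scaling to 100 subject-years, as "calculated as the number of subjects with AEs divided by the total time at risk across all subjects in the given treatment arm". The denominator follows: "Time at risk for a subject is calculated as time from first dose to 28 days following the last dose of IMP". Exact Poisson 95% limits are attached. The summary has lines for any TEAE, serious TEAEs, AESIs and injection site reactions.

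SAP 16.1.1 gives no end date for the events that enter the rate. SAP 16.1 defines a TEAE by its start relative to first dose and sets no upper limit. Other sections do set limits:

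- SAP Section 6 lists the secondary safety endpoint as "Occurrences of treatment-emergent adverse events (TEAEs) and serious adverse events (SAEs) including and up to Week 52".
- SAP 15.1 states: "The primary endpoint is the occurrence of treatment-emergent AESIs (hypersensitivity) up to Week 52". SAP 16.2.3.1 repeats this.
- SAP Section 8 cuts the data for the final analysis at "up to week 52 date (or end of treatment date+28 days, whichever occurs later) for subjects who completed the study". For subjects who stopped treatment early, the cut is at "theoretical week 52 (ie 52 weeks after first intake) or 4 months safety follow-up visit, whichever occurs first".
- SAP Section 8 also says that all AE tables will be produced again with additional events. It does not say whether the time at risk changes.

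The on-treatment definitions in SAP 16.3 to 16.5 cover laboratory, vital sign and ECG summaries only.

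**The concern.** There are two separate faults.

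**Label against formula.** Events and subjects with events differ as soon as anyone has a repeat event, which is foreseeable with an injection every other week. An event rate needs all events in the numerator. A first-event incidence rate needs each affected subject's time to end at that event. The SAP counts subjects but lets their time run on, so the quantity is neither. The label also says exposure to IMP, although the time includes 28 days after the last dose.

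**Window.** For completers the data cut and the time at risk coincide. For early terminators, the time stops at last dose + 28 days while their data are kept for longer. Such subjects exist by design: the SAP says that Week 24 non-responders stop IMP but stay in the safety assessments. Their off-drug events can enter the numerator with no time to match.

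The primary objective is comparative safety, and this rate with its interval sits on the lines of the main AE summary. A reader who trusts the label would take it for something it is not.

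**Working it through.** The SAP states no numerical rate, so there is no figure of the plan's own to reproduce.

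**1. Size of the label/formula fault**

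Inputs: AESI incidences of 11% (rash) and 26% (injection site reactions) from SAP 7.1; SAE 15-17% and TEAE up to 91% from Protocol 5.2.3.3. Assumptions: constant hazard, one full year per subject.

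- SAP rate per 100 subject-years = 100p
- First-event rate per 100 subject-years = 100 × [−ln(1 − p)]
- Shortfall = 1 − p / [−ln(1 − p)]

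| p | SAP rate | First-event rate | Shortfall |
|---|---|---|---|
| 0.11 | 11.0 | 11.7 | 5.6% |
| 0.15 | 15.0 | 16.3 | 7.7% |
| 0.17 | 17.0 | 18.6 | 8.8% |
| 0.26 | 26.0 | 30.1 | 13.7% |
| 0.91 | 91.0 | 240.8 | 62.2% |

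The interval fits badly at the top end too. With 118 of 130 subjects affected (91%), the exact Poisson limits on the count are 97.7 to 141.3, so the upper limit exceeds the number of subjects in the arm.

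**2. Window for one subject**

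Inputs: last planned dose at Week 48 (Protocol Table 1, footnote g); 1 month = 30.4375 days (SAP 11.8), so 4 months = 121.75 days.

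- Completer: last dose on day 336; 336 + 28 = 364 days at risk; Week 52 = 364 days. No gap.
- Last dose at Week 24: 168 + 28 = 196 days at risk. The data cut is min(364, 168 + 121.75) = 289.75 days. Gap = 93.75 days.

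**3. Window per arm**

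Assumptions: 130 per arm; 20% early termination (26 early, 104 completers); every early terminator followed to the data cut. The 20% is borrowed from the drop-out allowance in SAP 7.1. The maximum gap is 93.75 / 7 = 13.39 weeks. It applies to last doses at Weeks 0 to 34 and then shrinks to 12, 10, 8, 6, 4 and 2 weeks for last doses at Weeks 36 to 46.

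| Timing of last dose | Time at risk (weeks) | Unmatched (weeks) | Share |
|---|---|---|---|
| Even over Weeks 0-46 | 104×52 + 26×27 = 6110 | 26 × 11.80 = 306.7 | 5.0% |
| All at Week 24 | 104×52 + 26×28 = 6136 | 26 × 13.39 = 348.2 | 5.7% |
| All at Week 0 | 104×52 + 26×4 = 5512 | 348.2 | 6.3% |

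With the even spread, 10% and 30% early termination give 2.4% and 8.0%. All these shares fall if subjects leave the study, because they then contribute no late events.

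**4. Re-produced tables, only if the same denominator is kept**

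A completer would then have events counted for a further 121.75 − 28 = 93.75 days against 364 days at risk.

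**The case against.** **The formula is explicit, so only one word is wrong.** The table is introduced as a count of subjects, and programmers would compute the same ratio. This stands in part: for a given set of events the arithmetic is clear. But the rate would still be published under the wrong name, and which events belong to it is not stated.

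**Subjects over total time is a legitimate descriptive ratio, and the SAP never claims a first-event rate.** This is fair. The shortfalls above are measured against a yardstick, not against a promise in the plan. The 62% needs a constant hazard and the highest TEAE figure cited. For SAEs the gap of 8-9% is small beside sampling error: with 20 affected subjects of 130, the exact Poisson interval runs from about 39% below to 54% above the estimate.

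**The window mismatch is inferred.** This also stands to a degree. A reader might infer that the SAP orders late events into the rate. It does not say so; someone could equally take time at risk as limiting which events count. What the documents support is narrower: no text in 16.1 or 16.1.1 imposes that limit, and the retained data run past it.

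**Stronger readings that the documents do not support:**

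- That about 5% is a ceiling. It depends on when dosing stops; clustering at Week 24 or earlier gives more.
- That completers are misaligned in the re-produced tables. The SAP leaves that denominator open.
- That the comparison of arms is biased. Both arms use the same formula, no rate ratio or difference is planned, and no difference in early termination between arms has been shown.

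**Conclusion.** The point holds as a specification fault in a descriptive rate. The conflict between label and formula is on the face of SAP 16.1.1 and needs no assumption. Its size does: it rests on a constant hazard and a full year per subject, and is modest on the AESI and SAE lines and large only for very common categories such as any TEAE. The missing numerator window is a gap in the text. Its weight rests on the assumed share, timing and follow-up of early terminators, and is of the order of 5% to 6% of time at risk at 20% early termination.

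A reader might infer that the primary safety result is compromised. It is not: SAP 15.1 uses proportions of subjects with Clopper-Pearson intervals, and neither ACR20 nor the sample size touches this rate. Subject counts, AE listings and treatment duration are also reported, so part of the correct picture could be rebuilt. Severity is minor to should-fix.

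**What to change.** Revise SAP 16.1.1 so that label, formula and window agree. Choose one:

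- **(a) First-event rate.** Subjects with a first event, divided by time to that event, or to last dose + 28 days if there is none. Label it subjects per 100 subject-years and keep the exact Poisson interval.
- **(b) Event rate.** All events divided by total time at risk. Label it events per 100 subject-years, with an interval that allows for repeat events within a subject.

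Under either choice, restrict the numerator of the rate to onsets from first dose to last dose + 28 days, in the main tables and in any re-produced tables that carry the rate.

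The restriction must apply to the rate only. Leave subject counts and percentages on their existing windows: Week 52 for the endpoints, and the 4-month visit in the re-produced tables. Cutting the counts as well would set the AESI line at odds with SAP 15.1 and drop off-drug events in subjects deliberately kept in safety follow-up. Add a footnote that later events are counted but not included in the rate.

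The cost is SAP wording and minor programming. No new data, visits or subjects are needed.

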### 5.2.3.3 Other Secondary Endpoints

#### Safety

#### **Incidence of TEAEs and SAEs including and up to Week 52**

In a population of MTX insufficient responders, the rate of TEAEs and SAEs at Week 52 has been reported up to 91% and 15-17%, respectively (40, 41, 42).

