## 8 Statistics

### 8.1 Sample Size

According to EMA recommendation (EMA/CHMP/SAWP/200743/2016), a total of 100 patients/arm should be adequate for a study primarily focusing on safety. To account for drop outs, this descriptive study will include 260 randomized patients in total (130/arm) in order to ensure 200 subjects in the study at Week 52. In fact, based on averaged originator's dropout rates at Week 52, a 20% rate of drop-out overall is included in the sample size (29, 40, 41). This sample size will permit an informative assessment of the occurrence of most common AESI (> 1/10) such as injection site reactions, and rash with a precision of 12.0% and 9.0% for the AESIs incidence of 26.0% and 11.0% respectively (29).

A subset of 60 patients (30 per treatment arm) will be randomly selected to participate in population PK analysis.

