11.1 Descriptive Methods

Descriptive statistics for continuous data will include the following:

- Number of subjects with non-missing data (n)
- Number of subjects with missing data
- Mean, standard deviation (SD)
- Median, first and third quartiles (Q1 and Q3)
- Minimum and maximum
- 95% confidence interval (CI).

All statistics will be rounded according to Merck's Global Biostatistics Output Standards (GBSOS) Booklet (Version 4.0 or later), ie, percentages will be rounded to one decimal. The mean, median, Q1, Q3, and 95% CI will be presented with one additional decimal compared to the raw data; SD will be presented with two additional decimals compared to the raw data; and minimum and maximum will be presented with the same number of decimals as the raw data.

All data will be presented by nominal visit (including the safety follow-up visits – four weeks and four months after the last dose of IMP) and no visit windowing rules will be implemented. Data from unscheduled visits will be listed but will not be included in summaries presented by

visit. The exceptions will be in the calculation of the baseline values. Data from unscheduled visits will also be included in the calculation of the worst on-treatment values and grades.

Categorical data will be summarized by presenting the number of subjects with non-missing data (n), the number of subjects with missing data (missing), and the number and percentage of subjects in each category. Percentages will be based on the number of subjects with non-missing data in the analysis set of interest, unless otherwise specified.

Time to event variables will be summarized by presenting Kaplan Meier estimates and 95% CIs.

Change from baseline will be calculated as the post-baseline value minus the baseline value. Percent change from baseline is defined as (100 x (post-baseline – baseline) / baseline).

If all baseline values are missing for a particular variable, the change from baseline and percent change/percent improvement from baseline will not be calculated.

A 2-sided significance level of 5% will be used for all analyses. Two-sided 95% confidence intervals will be calculated.

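### SAP 16.1.1 puts an exact Poisson interval on a count of subjects over time at risk that is not stopped at the first event; the interval is too wide for frequent rows, about threefold for any TEAE at 91%.

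*SAP*

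**What the plan says.** SAP 16.1.1 introduces the rate as a number of events per 100 subject-years, but the calculation that follows counts subjects: "calculated as the number of subjects with AEs divided by the total time at risk across all subjects in the given treatment arm". The denominator is full exposure: "Time at risk for a subject is calculated as time from first dose to 28 days following the last dose of IMP". Nothing stops a subject's clock at the first event of the category. The interval rule is "Two-sided 95% CIs for incidence rates will be provided using the exact Poisson method", and it applies to every row of the overall summary, from any TEAE down to deaths and injection site reactions.

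For the primary endpoint, SAP 15.1 treats a subject count differently. The proportion with an AESI in each arm gets "Exact 95% CIs, calculated with the Clopper-Pearson method", and for the most commonly observed AESI events it adds the half width of the 95% interval for the between-arm difference.

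SAP 11.1 sets the level ("A 2-sided significance level of 5% will be used for all analyses") and asks for two-sided 95% intervals in general. For categorical data it lists only counts and percentages and names no interval method. In the text available, the Poisson interval is therefore the only one named for overall TEAEs and SAEs. SAP Section 18 (the IDMC analyses) is not in that text and could not be checked.

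**The concern.** An exact Poisson interval assumes a count with no upper bound and with variance equal to its mean. A count of subjects with at least one event cannot exceed the arm size, and its variance is near n·p·(1-p), not n·p. The two agree when p is small and part company as p approaches 1. If each subject's time at risk ended at the first event, the shorter denominator would make up for the cap. Here it does not, because the clock runs on. The fault is the combination of numerator, denominator and interval, not any one of them alone.

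At stake is the precision shown for the frequent rows of the table that describes overall comparative safety. In a descriptive trial of a proposed biosimilar, readers judge similarity partly from such intervals, and intervals that are too wide make two arms look more alike than the data warrant.

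**Working it through.** **Inputs.** Arm size, from Protocol 8.1: "260 randomized patients in total (130/arm) in order to ensure 200 subjects in the study at Week 52". Event shares, from Protocol 5.2.3.3: "the rate of TEAEs and SAEs at Week 52 has been reported up to 91% and 15-17%, respectively". Injection site reactions 26.0% and rash 11.0%, from Protocol 8.1 (Protocol 5.2.3.1 gives 26.5% for the former, which makes no difference here). The shares 80%, 70% and 50% are illustrative.

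**The plan's own figure.** The documents state no width for the Poisson intervals. The precision they do state, 12.0% and 9.0%, is for between-arm differences: 1.96·sqrt(2p(1-p)/n) with n = 100 gives 12.16% at p = 0.26 and 8.67% at p = 0.11, which agree after rounding to whole percent. Those figures do not depend on the Poisson rule.

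**Formulas.** For x subjects out of n:
- Exact Poisson limits on the count: chi-square(0.025; 2x)/2 and chi-square(0.975; 2x+2)/2.
- Clopper-Pearson limits on the proportion: beta(0.025; x, n-x+1) and beta(0.975; x+1, n-x).
- Large-sample width ratio: sqrt(np)/sqrt(np(1-p)) = 1/sqrt(1-p).

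Both intervals use the same person-time, so the width ratio is the same on the count, percentage or rate scale.

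**Results, n = 130, limits as % of the arm:**

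| Row | x | Poisson | Clopper-Pearson | Width ratio | 1/sqrt(1-p) |
|---|---|---|---|---|---|
| Any TEAE, 91% | 118 | 75.1 to 108.7 | 84.4 to 95.1 | 3.1 | 3.29 |
| 80% | 104 | 65.4 to 96.9 | 72.1 to 86.5 | 2.2 | 2.24 |
| 70% | 91 | 56.4 to 85.9 | 61.3 to 77.7 | 1.8 | 1.83 |
| 50% | 65 | 38.6 to 63.7 | 41.1 to 58.9 | 1.4 | 1.41 |
| Injection site reactions, 26% | 34 | 18.1 to 36.5 | 18.8 to 34.6 | 1.17 | 1.16 |
| SAE, 17% | 22 | 10.6 to 25.6 | 10.9 to 24.5 | 1.11 | 1.10 |
| SAE, 15% | 20 | 9.4 to 23.8 | 9.7 to 22.8 | 1.10 | 1.09 |
| Rash, 11% | 14 | 5.9 to 18.1 | 6.0 to 17.4 | 1.07 | 1.06 |

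For any TEAE the Poisson limits are 97.7 to 141.3 subjects in an arm of 130; Clopper-Pearson gives 109.8 to 123.7. The Poisson upper limit first exceeds the arm size at x = 108 (83%), where it is 130.4. With 100 per arm the ratio at 91% is 3.15, and impossible limits start at 81 subjects.

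**Rate scale.** The documents give no mean time at risk. Assuming 0.8, 0.9 or 1.0 year, the upper limit for any TEAE is 135.9, 120.8 or 108.7 per 100 subject-years. The highest attainable value (every subject affected) is 100 divided by mean time: 125.0, 111.1 or 100.0. The limit exceeds it each time.

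**Coverage of the nominal 95% Poisson interval** under binomial sampling is about 100% at 91%, 98.4% at 26% and 98.1% at 15% and 17%.

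**Time at risk stopped at the first event.** With a constant hazard and 91% incidence, simulated coverage of the exact Poisson interval is 95.2%. The method is sound once the denominator matches the numerator.

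**The case against.** The strongest reply is that this is a supporting table in a descriptive trial with no test, margin or decision rule attached. The error is conservative, the counts are printed beside the rates, and most rows are infrequent enough for Poisson and binomial limits nearly to coincide. All of that stands, and it limits the weight of the point.

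Several stronger readings are tempting but not supported:
- *That the threefold excess applies across the table.* It applies only near 90%. The one documented figure that high is for any TEAE, and the protocol gives it as a maximum. For SAEs and injection site reactions the excess is 10 to 17% and no limit is impossible. The documents give no rates for the Grade 1, Grade 2 or drug-related rows.
- *That these are the only intervals planned for injection site reactions.* The protocol treats those as the commonest AESI event, so SAP 15.1 plans the half width for the difference, subject to a cut-off still to be set. Those that fall within the AESI definition also count in the Clopper-Pearson proportion.
- *That the Poisson interval would be too narrow because events cluster within subjects.* That concerns a count of all events, which the SAP does not compute, and the documents give no inputs for it.
- *That real differences between the products will be hidden.* This depends on the gap. At 118 against 100 of 130 (91% and 77%), Clopper-Pearson limits separate (84.4 to 95.1% and 68.7 to 83.9%) while Poisson limits overlap (75.1 to 108.7% and 62.6 to 93.6%). At 118 against 104 (91% and 80%), even the Clopper-Pearson limits overlap.

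Two further objections are fair. An event can end treatment and so shorten time at risk, which makes the binomial model approximate. And replacing the interval by Clopper-Pearson alone would leave the planned exposure-adjusted rate without a valid interval, which matters when the protocol says "a 20% rate of drop-out overall is included in the sample size".

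**Conclusion.** The point holds for frequent rows. As written, SAP 16.1.1 gives intervals too wide by about 1/sqrt(1-p): roughly threefold for any TEAE if its share is near 91%, about twofold at 70 to 80%, 1.4-fold at 50%, and 10 to 17% for SAEs and injection site reactions. Limits above the arm size arise only from 108 of 130 subjects. Coverage errs on the high side. The primary AESI proportion in SAP 15.1 is not affected.

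This rests on 130 per arm in the safety set, on follow-up little shortened by the events themselves, and, for the largest figure, on the protocol's upper value for TEAEs. It is worth correcting before the table is produced: a 95% limit that exceeds the number of subjects is a visible and avoidable error, and for overall TEAEs and SAEs no other interval is named in the text available.

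**What to change.** In SAP 16.1.1:
1. For the subject-based rate per 100 subject-years, end each subject's time at risk at the first event of the row's category (otherwise at 28 days after the last dose) and keep the exact Poisson interval. This preserves an exposure-adjusted rate with about 95% coverage.
2. In addition or instead, give Clopper-Pearson intervals for the proportion of subjects with at least one event in each row, as SAP 15.1 does for AESIs. If this is the only change, do not attach the Poisson interval to the rate over full exposure.
3. Describe the numerator as subjects with at least one event, so that the label matches the calculation.

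The cost is SAP wording and minor reprogramming: a separate time at risk for each row, and no new data. First-event rates will be numerically higher than rates over full exposure, markedly so for frequent rows. With one year of follow-up and a constant hazard, a 91% share gives -ln(0.09) = 2.41, or 241 per 100 subject-years against 91; a 26% share gives -ln(0.74) = 0.301, or 30 against 26. A footnote should state the definition, because these rates are not comparable with ones computed over full exposure.
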